- b.) Limited physical exam with a foot exam completed by the PI and /or the Co-investigator
- c.) Adverse Event Reporting collecting any problems or symptoms or significant events that have occurred since follow up visit 1, including any unscheduled hospital or primary care provider visits. Review Medical Records for changes in medical/surgical history.
- c.) Collection of diary cards
- d.) 2D Photographs of both feet for a visual assessment of your skin and soft tissue thickness
- e.) Foot Assessment Questionnaires: (FAAM, Mayo Clinical Scoring System, AOFAS Score, Manchester, and Pittsburgh Foot Survey) pertaining to foot pain and activity assessments.
- f.) Collection of diary cards

- g.) Device survey questions about the fit and feel of the device
- h.) PopSole™ Device removal

2. Upload a copy of all materials used to collect data about subjects: (Attach all surveys, interview/focus group scripts, and data collection forms except for case report forms, SCID or KSADS):

Document	Category Date Document Modified History
PopSole 6 and 10 week Phone Script Cohort 2_11.06.2020.docx(0.01)	Data Collection 11/6/2020 History
view Pittsburgh Foot Survey(2)	Data Collection 9/28/2020 History
√iew MAYO(2)	Data Collection 9/28/2020 History
view PopSole2 48hr phone follow up.doc(1)	Data Collection 7/21/2020 History
view AOFAS Questionnaire.docx(1)	Data 4/8/2020 History Collection
view FAAM Questionnaire(1)	Data Collection ² /19/2020 History
view Foot Survey(1)	Data Collection ^{2/19/2020} History
view Manchester Pain Questionnaire(1)	Data Collection ^{2/19/2020} History
View Mayo Clinical Scoring System(1)	Data Collection 2/19/2020 History
View PopSole TM Device Survey(1)	Data Collection 2/19/2020 History

 $\boldsymbol{\Im}_{\star}$ * Will blood samples be obtained for research purposes?

O Yes
No

Consent Process

Enter N/A in response to the following questions if a Waiver of Consent is requested for all research activities or if no subjects are being enrolled.

1. * Indicate where the consent process will take place and at what point consent will be obtained:

Clinical candidates with relevant foot pain who are interested in hearing more about the study will be referred from [name] clinical practice. The coordinators will be obtaining verbal consent from referred potential subjects through a telephone script, before asking the initial screening eligibility questions.

Once participants are found to be eligible and express their continued desire to participate in the study, an in person visit will be scheduled at one of the two clinic locations. Consent will be obtained by the physician investigator or his clinical designee's, which may include [name], DMP, [name], PA-C, [name], PA-C or [name] DPT with assistance from the study coordinator, prior to any research procedures being conducted during the screening/baseline visit. [name] clinical designees have significant experience with diagnosis and treatment of foot and heel pain (see section 5 below).

2. * Describe the steps that will be taken to minimize coercion and undue influence, including assurance that there is sufficient time for subjects to make an informed decision:

Once a patient has been identified/confirmed by the principal investigator as an appropriate candidate, the patient will be scheduled for the consent/screening visit. This screening visit will take place at UPMC Aesthetic Plastic Surgery Center located at [name] or the UPMC Lemieux Sports Medicine Complex in [name] and will include review of the informed consent.

The physician investigator or co-investigator, with assistance from the research coordinator, will discuss with the subject the nature of the research study, design schema, the risks and benefits, cost and payments and rights as a research subject participant. The potential subject will review the informed consent document allowing ample time to review all information and ask questions. Should the potential subject wish to take the consent and review it outside of the office setting or discuss with other family or medical personnel, he/she will be able to leave the office and return at a later date. The physician investigator will provide the potential subject a private area to conduct this informed consent document review prior to signing the informed consent. After this detailed discussion of the study and conclusion of any and all questions, the study investigator, will obtain informed consent.

The research coordinator will document the consenting process into the research chart and prior to beginning any research activities provide a copy of the fully executed, informed consent document to the subject for his or her records. No research related procedures will be performed before the informed consent has

been obtained.

It will be explained that their choice, to participate or not participate, will not affect their current relationship with the referring plastic surgeon, orthopaedic surgeon, podiatrist or UPMC.

3. For studies that involve multiple visits, describe the process to ensure ongoing consent:

Ongoing consent assessment of voluntary consent desired by the subject will be conducted verbally at each visit, reminding subjects that their continued participation is voluntary and may be terminated at any point. The subject's continued consent will be documented contemporaneously. This process will be documented in the coordinator's visit note.

4. * Steps to be taken to ensure the subjects' understanding:

The physician investigator or co-investigator will discuss with the subject the nature of the research study, design schema, the risks and benefits, cost and payments and their rights as a research subject. Technical terms will be described using lay terminology and subjects will be encouraged to ask questions, and all will be answered to their satisfaction.

The potential subject will review the informed consent document allowing ample time to review all information and ask questions. The study investigator will provide the potential subject a private area to conduct this study document review prior to signing the informed consent. After this detailed discussion of the study and conclusion of any questions, the physician investigator, will obtain informed consent. The research coordinator will document the consenting process and prior to beginning any research activities provide a copy of the fully executed informed consent document to the subject for his or her records.

5. * Are you requesting an exception to the IRB policy related to the informed consent process:

Yes O No

* Provide a justification and describe the qualifications of the individuals who will obtain consent:

The consent may be reviewed with the participant by the MD/PI. In addition, the consent discussion may be performed by three co-investigators who are also clinical designees as well. Firstly, one designee is an experienced MD who is well versed with the PopSole device. [name], DPM is listed as an innovator for the device. She is a board certified licensed podiatrist and she has been a collaborater/co-investigator on numerous research studies. She has been in practice for over 20 years.

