We propose a proof of concept clinical trial to assess the validity of a novel foot offloading device (PopSole™) that allows for customized pocketing out of areas of pain, along with customized arch support and metatarsal height to optimize offloading.

An important part of recovery from foot injury (including fat injections, treatment of diabetic ulcers, wart removal, painful calluses, healing fractures) is the minimization of pressure to optimize healing. This offloading is challenging because current modalities limit patient function, work, and safety due to their bulk, weight, and attractiveness. (7) Aggressive modifications to shoe soles create asymmetry between the feet that can lead to gait instability, falls, and pelvic shifts. (8-15) We have another clinical trial to assess comparison of this device to our current standard of care method utilizing cutting metatarsal pads and adhering them to current insoles to reduce pressure on grafted areas, but this does not adequately reduce pressure on the fat grafted areas.

Our device can be used in conjunction with post-operative boots that have flat bottoms to augment them for more comfort and potentially enable earlier transition to regular shoe gear. It may be able to eliminate more bulky devices completely as PopSole™ can fit into a regular sneaker or dress shoe.

With our novel device PopSole™, we aim to expedite the recovery process, reduce pain, and reduce compensatory gait issues that could lead to falls. Patient balance and stability is a big concern with the presently available offloading modalities. Falls and injuries have been experienced by patients, especially elderly, neuropathic diabetic patients and physically challenged individuals. In addition, our device can be easily placed in a slide-on shoe for wear around the house, or in the shower.

Our primary aim of this validation project is to allow patients with foot pain to trial the device for 4 weeks to assess improvements in pain, assess fit and feel, durability, and compliance. This project will allow for modifications of the device to be made prior to future randomized studies to assess pressure and gait assessment, shear forces, and use in the diabetic population.

View: Pitt SF: Study Design

Study Design

1. Total number of subjects to be enrolled at this site (enter -1 for chart reviews, banking, registries):

20

2. Describe and explain the study design:

This is a prospective proof of concept study.

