Describe the primary and secondary study endpoints:

Primary Outcomes: Pain scores as assessed by validated outcomes measures, compliance over 4 weeks, durability of the device (do the bubbles hold up or require replacement).

Secondary Outcomes: Satisfaction with using the device, difficulties with the use of the device.

4. Provide a description of the following study timelines:

Duration of an individual subject's active participation:

Cohort 1: 4 Weeks

Cohort 2: 3 Months

Duration anticipated to enroll all subjects:

6 months

Estimated date for the investigator to complete this study (complete primary analyses):

6/30/2020

5. List the inclusion criteria:

Patients meeting the following criteria will be eligible to participate in the study:

- 1. Aged 18 years or older and able to provide informed consent
- 2. Subjects with foot pain due to forefoot or heel fat pad atrophy or chronic plantar fasciitis as defined by heel pain for greater than 6 months and failed non-surgical therapy
- 3. Willing and able to comply with follow up examinations

6. List the exclusion criteria:

Patients with the following characteristics will be excluded from participating in the study:

- 1. Concurrent injury to the lower extremity that would effect gait
- 2. Open foot ulcerations, fractures, or diagnosis of osteomyelitis of the feet
- 3. Surgical foot intervention in the last 6 months
- 4. Diagnosis of pregnancy or the intent of the participant to become pregnant during participation in this study
- 5. Neuropathy

- 6. Any issue that per the physician's determination would render the patient not appropriate to continue participation in the study (compliance, change in physical status, etc.)
- 7. Will children or any gender, racial or ethnic subgroups be explicitly excluded from participation?
 - Yes O No
 - * Identify the subgroups and provide a justification:

As foot pain due to forefoot or heel fat pad atrophy or chronic plantar fasciitis generally is not common in children, we will be limiting our population to adults 18 years of age or older.

8. Describe the power analysis used and cite your method of statistical analysis. If a power analysis is not possible, thoroughly justify the sample size required for the study, including appropriate literature citation (alternatively provide page reference in attached protocol):

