Should the subject complete the informed consent process and screening procedures, the duration of time to complete is estimated to take approximately 1-2 hours and will include the following research procedures:

- 1.) Obtain Informed Consent to be completed by the Principal Investigator (PI) or designated Co-Investigator. Once completed the subject will be allocated a subject ID number. This number will be the unique identifier for the subject during his/her trial participation.
- 2.) Performance of a limited physical exam, inclusive of participant's foot exam with a gait and shoe gear evaluation to be completed by the PI and /or Co-investigator. Any prior foot injuries or previous foot ulcerations/skin breakdown will be assessed. The foot exam will include a vascular, neurologic, dermatologic and orthopedic baseline assessment. As part of the exam (for example, related to diagnosing plantar fasciitis), an ultrasound may be performed in the clinics per the investigators' discretion.
- 3.) Medical and surgical history collection: Past medical and surgical history will be

collected by referral report or subject report.

Should the physician require additional information for review to confirm study eligibility, the subject may be asked to obtain and provide medical records to assist with the PI's review.

- 4.) Collection of subject's vital signs (Temp, HR, Resp., BP), medication profile, allergies, height, weight, and BMI calculation.
- 5.) Collection of demographic information to include subject's date of birth, gender, race, ethnicity, education, and smoking history.

ELIGIBILITY DETERMINATION: The Principal Investigator and/or in consultation with the co-investigators will determine subject eligibility to participate in the study based on the inclusion/ exclusion criteria.

All subjects will receive the PopSole™ offloading device at the screening/baseline visit, be asked to wear it for 4 weeks, and will be asked to return for an in-person evaluation at V1 (Week 2) and a completion study visit at V2 (Week 4). There will also be a phone call 48 hours after the screening visit to ensure that the patient has no issues or concerns with wearing the device.

Subjects will complete the following screening research procedures:

- 1.) Baseline reported outcome measures (PROMs) questionnaires and surveys that will take approximately 25 minutes to complete:
- Foot and Ankle Ability Measure (FAAM) questionnaire to assess subject ADL and function ability

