- Manchester Foot and Ankle Disability Index to assess subject foot pain/discomfort
- Pittsburgh Foot Survey to assess subject pain, activity, life satisfaction/quality of life
- Mayo Clinical Scoring System questionnaire (MAYO) to assess subject pain, activity, and function (Investigator Rated)
- American Orthopaedic Foot and Ankle Society questionnaire (AOFAS) to assess subject pain and function (Investigator Rated)
- 2.) 2D Photographs of both feet will be performed for a visual baseline assessment of skin.
- 3.) Collection of subject's vital signs (Temp, HR, Resp., BP), medication profile, allergies, weight, BMI calculation and adverse event collection and reporting.
- 4.) Diary cards with instruction to start entry on the diary card 24 hours after the screening visit to continue through Visit 2 (Month 1) and be placed to study chart. The subject will be instructed to document self-assessment of the following events pertaining to the feet: Pain, Bruising, Redness of the skin, Itching, Swelling, Bleeding, Other (any concerns/issues not listed). The subject will be instructed to identify on the diary card the location, date, and day of each documented event. Unresolved events at Visit 2 will be carried over for documentation to the adverse event log.

5.) Offload Device Distribution to remain in use at all times during ambulation. Devices will be provided for both feet to maintain symmetry and gait stability between the two feet. One pair of devices will be given for use in shoe gear, and one pair will be given for use in a slide in the shower. A device instruction sheet will also be provided to the participants for reference.

48 Hour (+/- 1 Day) Phone Call

The study coordinator will call the subject 48 hours after the screening visit and eligibility determination. This phone call is to assess if there are any questions or concerns with the fit and feel of the PopSole device. If there are any issues that the subject may be experiencing the study coordinator will have an investigator or co-investigator reach out to the subject. The coordinator will be working off of a phone script, to ensure that all aspects of wearing the device have been addressed.

Follow up Visits:

Visit 1 (Week 2) with (+/- 7days) study window:

This visit will take approximately 1 hour and will take place at the Isaly's Medical Building- UPMC Aesthetic Surgery Center and/or UPMC Lemieux Sports Medicine Complex with the physician investigator and research team.

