Irritation of feet by the device. Difficultly of foot fitting in shoe with the device. The device may not offload the appropriate area and a new device may need to be provided, or modifications to the device may need to be made. Slippage of the device in foot gear. Feeling of asymmetry or one foot being higher than the other.

4. Other Risks:

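### The background links asymmetry between the feet to falls and the risk list names asymmetry and slippage for this insole, but falls are neither a listed device risk nor a named safety item

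*Combined protocol and SAP*

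**What the plan says.** The protocol touches on falls, or what precedes them, in five places.

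- **Background (Study Aims, item 2).** It gives a mechanism: "Aggressive modifications to shoe soles create asymmetry between the feet that can lead to gait instability, falls, and pelvic shifts". It then says "Patient balance and stability is a big concern with the presently available offloading modalities", followed by "Falls and injuries have been experienced by patients, especially elderly, neuropathic diabetic patients and physically challenged individuals".
- **Eligibility (Study Design, items 5 and 6).** The age criterion is "Aged 18 years or older and able to provide informed consent", with no upper limit. Exclusions include "Concurrent injury to the lower extremity that would effect gait", neuropathy, and a discretionary item for any issue that the physician considers disqualifying. No criterion mentions falls, balance or mobility.
- **Procedures (Research Activities, both cohorts).** Screening includes a limited physical examination, "inclusive of participant's foot exam with a gait and shoe gear evaluation". The insole is worn whenever the participant walks. Two pairs are supplied, one for shoes, and "one pair will be given for use in a slide in the shower".
- **Risks (Risk and Benefits, items 1 and 2).** The device risks, all classed as infrequent, end with: "Slippage of the device in foot gear. Feeling of asymmetry or one foot being higher than the other". Falls do not appear. Item 2 says that a device for each foot limits asymmetry and gait instability.
- **Safety collection (Research Activities).** The diary covers events of the feet: pain, bruising, redness, itching, swelling, bleeding and an Other category. Each follow-up visit has a general adverse-event question.

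**The concern.** The form asks for all risks that can reasonably be foreseen. The background describes a chain from asymmetry through instability to a fall. The risk section accepts the first link for this device and describes a mitigation for the second, but never names the third. A reader of the risk list alone would not learn that the authors had considered falls.

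Two things are at stake. First, the risk list should support the consent, so an omission there may carry over. Second, a fall that injures no foot may not strike a participant as belonging on a card about foot events, and may be forgotten by the next visit. In a study meant to find problems with the device before larger trials, and with difficulties of use as a secondary outcome, falls are worth asking about directly.

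**Working it through.** The plan gives no figure on this point and no arithmetic applies. The check sets the sections side by side.

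**1. Is the hazard tied to this device?**
- Mechanism (Study Aims, item 2): asymmetry, then gait instability, then falls.
- Asymmetry and slippage: both listed as risks of this device (Risk and Benefits, item 1).
- Gait instability: treated as something to limit by supplying devices for both feet (Research Activities, device distribution; Risk and Benefits, item 2).
- Falls: absent from the device risk list.

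The precursors are attributed to the insole and the consequence is stated elsewhere, so the omission is internal to the protocol.

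**2. Which of the named groups can enter?**
- Neuropathic diabetic patients: excluded by criterion 5.
- Elderly patients: no upper age limit.
- Physically challenged patients: criterion 1 applies only where a concurrent lower-limb injury affects gait.

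One of three groups is removed by a criterion specific to it. Members of the other two remain eligible unless another criterion, including discretionary criterion 6, applies to them. Gait is evaluated before the eligibility decision, but the text does not say how the finding is used beyond what criteria 1 and 6 imply.

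**3. What is the exposure?** All walking, plus a pair for a shower slide. Participation is 4 weeks in Cohort 1 and 3 months in Cohort 2.

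**4. How would a fall be recorded?**
- Diary: none of the six named events is a fall, and the card is limited to events of the feet. Other is the only place for it.
- Visits: the general adverse-event question, which also covers unscheduled hospital and primary care visits, would take in a fall that the participant mentions.
- Calls at 48 hours, and at Weeks 6 and 10 in Cohort 2: these concern fit and feel. The scripts are attachments and are not in the reviewed text.

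A fall can therefore be recorded, but nothing in the visible text asks about one by name.

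**The case against.** The strongest reply is that the fall history belongs to other devices. The background attaches it to existing modalities and blames bulk, weight and aggressive sole changes. This product is an insole for ordinary shoes, described as comparable to off-the-shelf insoles and of minimal risk, and intended to reduce gait problems. That stands as regards the fall history. It does not remove the gap, because the protocol's own risk list gives asymmetry and slippage for this insole and its own mitigation refers to gait instability.

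The safeguards also deserve credit: bilateral devices, modification or replacement of a poor fit, referral of problems raised on calls to an investigator, general adverse-event collection at every follow-up visit, and a gait, neurologic and orthopedic assessment before the eligibility decision.

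A reader might infer several stronger things that the documents do not support:

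- *Screening looks only for injury and neuropathy.* It also excludes ulcers, fractures, osteomyelitis, foot surgery in the past 6 months and pregnancy, and has the discretionary item.
- *Fall-prone people are enrolled.* The text shows only that some remain eligible.
- *Participants are not told of the risk.* The consent pages are not available here, and the consent process includes a discussion of risks. The call scripts, device survey and participant instructions are also unseen.
- *The trial fails to support a claim of fewer falls.* Falls are not an endpoint, and gait assessment is left to later studies.

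**Conclusion.** The point holds in a limited form. The background and the mitigation text treat instability and falls as a real concern. The device risk list stops at asymmetry and slippage, and safety collection does not ask about falls by name. Two of the three groups that the background singles out have no exclusion specific to them, and use is continuous and extends to the shower.

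The size is that of an inconsistency in wording with safety relevance, in a study of 20 people using a device classed as non-significant risk. No probability of a fall can be given, because the documents contain no fall rate; any percentage would rest wholly on an assumed one. The conclusion assumes that the visible risk list is complete and that the diary card follows its description in Research Activities. It does not depend on what the consent form or scripts say, though these should be checked.

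It does not follow that eligibility must be narrowed. Whether to restrict entry by balance or fall history is a clinical trade-off for the investigators.

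**What to change.** 1. **Risk list.** Reconcile Study Aims, item 2, and Risk and Benefits, item 2, with the device risks in Risk and Benefits, item 1, and its repeat in the Risk entry for offloading devices. Either list falls as a foreseeable risk or state why they are not one. Check that the consent form agrees.
2. **Safety collection.** Add any fall as a named item on the existing diary card and in the adverse-event question at each follow-up visit, and in the call scripts if it is not already there. In Cohort 2 the diary instruction ends at Visit 2 although cards are also collected at Visits 3 and 4, so the period that the new item covers should be made clear.
3. **Eligibility.** The investigators should reconcile the background with the Study Design criteria and state how the screening gait evaluation informs the eligibility decision. No criterion or threshold is proposed here.

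The cost is wording in a few documents, a slightly longer risk list and a few more events to record. No new procedure is needed, since gait is already evaluated and the diary, calls and visits already exist.
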